10.7.1.1 Demographic and Background Assessments

The following demographic and background assessments will be performed during the study at the time-points specified in [Table 10.7.1](#).

10.7.1.1.1 Demographics

Demographic data: age, year of birth, gender, race, height, weight and BMI.

Height in metres (m) (to the nearest centimetre (cm)) and weight in kilogram (kg) (to the nearest 0.1 kg) in indoor clothing and without shoes will be measured. BMI = body weight (kg) / [height (m)]² will be calculated.

10.7.1.1.2 Medical History and Concurrent Conditions

Relevant medical history and current conditions will be recorded in the eCRF.

10.7.1.1.3 Virology Tests

Virology tests: HBsAg, HCV Ab and HIV (antibodies to HIV-1 and HIV-2).

HBsAg, HCV Ab, and HIV (antibodies to HIV-1 and HIV-2) virology tests will be analysed from the same serum sample for biochemistry analyses at Screening by Simbec-Orion Laboratory Services , using the Roche cobas® c6000 analyser series comprising of the c501 and e601 modules or any other appropriate analyser.

10.7.1.1.4 Drugs of Abuse (including Alcohol and Cotinine)

Urine DOA screen (including alcohol and cotinine): Alcohol, amphetamines, barbiturate, benzodiazepine, cannabinoids, cocaine, cotinine, methadone, and opiate.

A **mid-stream** urine sample will be collected into a universal collection/storage container. At protocol-defined time-points when both urinalysis and drugs of abuse / alcohol screening are required, all urine analyses will be performed from a single approximately 20 mL urine sample.

Urine samples for drugs of abuse (including alcohol and cotinine) will be analysed by Simbec-Orion Laboratory Services, using the Roche cobas® c6000 analyser series comprising of the c501 and e601 modules or any other appropriate analyser. Assessments of urine sample quality (i.e., urine sample verification) will be performed by measuring urine creatinine for DOA.

10.7.1.1.5 Pregnancy Test, Menstrual and Obstetric History

Pregnancy tests will be performed on all female participants. Pregnancy tests will be performed by Simbec-Orion Laboratory Services. Serum pregnancy tests will be performed at time-points specified in [Table 10.7.1](#). Urine pregnancy tests will be performed manually using appropriate urine pregnancy test kits at time-points specified in [Table 10.7.1](#).

Serum FSH to confirm post-menopausal status will be analysed from the same serum sample for biochemistry analyses at Screening for postmenopausal females only. Serum FSH analysis will be performed by Simbec-Orion Laboratory Services using the Roche cobas® c6000 analyser series comprising of the c501 and e601 modules or any other appropriate analyser.

10.7.1.2 Compliance with Inclusion/Exclusion Criteria

An Investigator will assess all participants against the study inclusion and exclusion criteria at Screening. Compliance will be re-confirmed on prior to each dose administration.

10.7.1.3 Safety Assessments

The following safety assessments will be performed at the time-points specified in [Table 10.7.1](#).

10.7.1.3.1 Adverse Events

AEs and SAEs that occurred during the study along with their severity and relationship to study drug will be reported.

An AE is defined as per Statutory Instrument 2004 No. 1031^[4]:

Any untoward medical occurrence¹ in a participant to whom a medicinal product has been administered, including occurrences which are not necessarily caused by or related to that product.²

Notes:

¹ Whether subjective complaint or objective finding.

² An AE can therefore be any unfavourable and unintended sign (including an abnormal laboratory finding), symptom, or disease temporarily associated with the use of an IMP, whether or not considered related to the IMP.

An unexpected adverse reaction is defined as:

An adverse reaction, the nature, or severity of which is not consistent with the applicable product information (e.g., Investigator's brochure for an unapproved investigational product or summary of product characteristics (SmPC) for an authorised product).

AEs will be monitored throughout the study from the signature of participant informed consent through to the post-study follow-up visit. All AEs will be recorded, whether considered minor or serious, drug-related or not.

All abnormal laboratory findings considered to be clinically significant will be recorded as AEs.

Recording of Adverse Events

All of the following details will be recorded in the participant's eCRF for each AE:

- Full description of AE.
- Date and time of onset.
- Date and time of resolution.
- Severity of event to be assessed by an Investigator in accordance with the definitions below.
- Relationship to IMP to be assessed by an Investigator in accordance with the definitions below.
- Action taken (if any).
- Outcome and details of any further follow-up.

Grades of Adverse Event Severity

The following grades will be used by an Investigator to describe the severity of AEs.

The following are the only grades, which will be used to describe AE severity. Only 1 severity grade will be used for each AE (e.g., mild - moderate is not acceptable).

SEVERITY OF THE AE	DEFINITION
Mild	The AE does not interfere with the participant's daily routines. It causes no more than slight discomfort or mild objective change in any of the safety parameters assessed during the study as determined by the Investigator.
Moderate	The AE interferes with some aspects of the participant's daily routines or moderate objective change in any of the safety parameters assessed during the study as determined by the Investigator.
Severe	The AE causes inability to carry out the participant's daily routine or severe objective change in any of the safety parameters assessed during the study as determined by the Investigator.

Definitions of Adverse Event Causality

The following definitions will be used by an Investigator to describe the relationship between an AE and the IMP.

The following are the only definitions which will be used to describe the relationship between AEs and the IMP. Only 1 relationship definition will be used for each AE (e.g., possible-probable is not acceptable).

RELATIONSHIP TO IMP	DEFINITION
Reasonable possibility of being related	
 There is a reasonable possibility of the event being related to the IMP. This might be temporal or due to a physiological or pharmacodynamic process
No reasonable possibility of being related.	
 No reasonable possibility of the event being related to the IMP, the IMP may not have been administered, no temporal relationship, and no known or understood physiological or pharmacological mechanism for the event to be related.

Adverse events of special interest

For this study, adverse events of special interest are:

- Bacteraemia proven to be caused by one of the vaccine strains
- Development of autoimmune diseases.

Should one of these events occur the PI (or delegate) will alert the Sponsor's Responsible Physician within 24 hours of becoming aware.

Serious Adverse Events

SAEs are defined in Statutory Instrument 2004 No. 1031 as any AE that

- a. results in death,

Note: Death is an outcome (of an AE, of progressive disease, etc.) and not an AE in itself.

b. is life-threatening,

A life-threatening event places the patient at risk of death at the time of the event. It does not refer to an event which hypothetically might have caused death if it were more severe.

c. requires hospitalisation or prolongation of existing inpatients' hospitalisation,

"In-patient hospitalisation" means that the patient has been formally admitted to a hospital for medical reasons, for any length of time. It does not include presentation to or care within an emergency department.

Complications that occur during hospitalisations are AEs. If a complication prolongs hospitalization, it is an SAE.

d. results in persistent or significant disability or incapacity, or

e. consists of a congenital anomaly or birth defect.

f. Is a medically important event or reaction.

Some medical events may jeopardise the participant or may require an intervention to prevent one of the above characteristics/consequences. Such events (referred to as 'important medical events') should also be considered as 'serious' in accordance with the definition.

SAEs must be reported within 24 h of knowledge of the event by submitting an initial SAE report via email or fax to Diamond Pharma Services Ltd.

E mail: [contact]

SAE [contact]

Suspected Unexpected Serious Adverse Reactions

AEs which meet all of the following criteria

- Serious.
- Unexpected (i.e. is not consistent with the applicable product information e.g., Investigator's brochure for an unapproved IMP or SmPC) for an authorised product.
- There is at least a reasonable possibility that there is a causal relationship between the event and the medicinal product (possible, probable, almost definite).

will be classified as SUSARs and will be reported to the REC and to the MHRA in accordance with applicable regulatory requirements for expedited reporting. It is the Sponsor's responsibility to report SUSARs to the REC and MHRA.

To ensure no confusion or misunderstanding of the difference between the terms "serious" and "severe," which are not synonymous, the following note of clarification is provided:

The term "severe" is often used to describe the severity of a specific event (as in mild, moderate, or severe myocardial infarction); the event itself, however, may be of relatively minor medical significance (such as severe headache). This is not the same as "serious," which is based on participant/event outcome or action criteria usually associated with events that pose

a threat to a participant's life or functioning. Seriousness (not severity) serves as a guide for defining regulatory reporting obligations.

Monitoring of Participants with Adverse Events

In the event of any abnormalities considered to be clinically significant by the investigating physician, participants will be followed up with appropriate medical management until:

- It has resolved/returned to normal or baseline.
- The event has stabilised at a level acceptable to the Investigator and is not considered to be clinically significant.

Pregnancy

Pregnancies must be reported within 24 h of knowledge and should be followed up to determine outcome, including spontaneous or voluntary termination, details of the birth, and the presence or absence of any birth defects, congenital abnormalities, or maternal and/or AEs that occur in the new born child(e.g., meconium ileus, respiratory distress).

Pregnancy outcomes must be collected for females who took the IMP and the female partners of any males who took the IMP. Consent to report information regarding these pregnancy outcomes should be obtained from the mother.

10.7.1.3.2 Laboratory Safety Assessments

Laboratory Safety Screen

Laboratory safety screen samples will be analysed by Simbec-Orion Laboratory Services. Printed laboratory test result reports will include normal reference ranges. A decision regarding whether the laboratory test result outside the normal reference range is of clinical significance or not shall be made by an Investigator/designee and the report will be annotated accordingly. Clinically significant laboratory test result abnormalities will be recorded on the AE page. The normal reference ranges for laboratory test parameters will also be filed in the ISF.

Biochemistry Tests: Alanine transaminase, albumin, alkaline phosphatase, aspartate transaminase, bicarbonate, total bilirubin, direct bilirubin, calcium, cholesterol, chloride, creatinine, creatine kinase, c-reactive protein, glucose (random), gamma glutamyl transferase, total globulin, lactate dehydrogenase, potassium, inorganic phosphorus (or phosphate), total protein, triglycerides, sodium, urea and uric acid.

Blood samples for biochemistry analyses for each time-point will be collected into an appropriately sized serum collection tube with or without a separator, and analysed by Simbec-Orion Laboratory Services using the Roche cobas® c6000 analyser series comprising of c501 and e601 modules or any other appropriate analyser. Assessments of blood sample quality (i.e., for sample verification) will be performed by measuring 3 indices [namely, Lipaemic (for Lipaemia), Haemolytic (for Haemolysis) and Icteric (for Icterus)] in serum.

Haematology Tests: Haemoglobin, haematocrit, mean corpuscular volume, mean corpuscular haemoglobin, mean corpuscular haemoglobin concentration, platelets, red blood cell count, red blood cell distribution width, WBC count, and WBC differential count (neutrophils,

lymphocytes, monocytes, eosinophils, and basophils) (reported in absolute and percentage values).

Blood samples for haematology analyses for each time-point will be collected into a collection tube containing ethylenediaminetetraacetic acid and analysed by Simbec-Orion Laboratory Services using the Siemens ADVIA® 2120 or Siemens ADVIA® or an any other appropriate analyser.

Urinalysis Tests: Specific gravity, pH, protein, glucose, ketones (or ketone bodies), urobilinogen, bilirubin, blood, leukocytes, and nitrite.

A mid-stream urine sample for each time-point will be collected into a universal collection/storage container and divided into aliquots. Urinalysis will be performed by Simbec-Orion Laboratory Services, using the Roche cobas® U6500 or any other appropriate analyser.

In the event that the urinalysis automated 'dipstick' test result is positive for nitrites and/or 2+ or more reported for protein, blood, and/or leucocytes, then urine microscopy will be performed. The following test parameters will be reported: bacteria, casts (non-pathogenic), casts (pathogenic), crystals, epithelial cells, red blood cells and white blood cells. The urine microscopy will be performed by Simbec-Orion Laboratory Services, using the Roche cobas® U6500 701 module or any other appropriate analyser/method. Separate aliquot samples will be sent for culture, if microscopy visualises bacteria (please refer to the Sample Handling Manual for processing and shipping instructions).

10.7.1.3.3 Other Safety Assessments

Vital signs: Systolic/diastolic blood pressure, pulse rate, oral body temperature. Measurements will be recorded in the supine position. Blood pressure, pulse rate and oral body temperature will be measured by the DINAMAP* Compact Vital Signs Monitor (Model TS) or equivalent. Normal ranges for vital signs are presented in [Appendix 2](#).

Physical Examination: A physical examination will be performed by an Investigator. The examination will include ear/nose/throat, ophthalmological, dermatological, cardiovascular, respiratory, gastrointestinal, central nervous system, lymph nodes and musculoskeletal). An Investigator can examine other body systems if required, at their discretion.

12-Lead ECG: Heart rate, PR interval, QRS width, QT interval and QT interval corrected using Bazett's formula and Fridericia's formula.

12-lead ECG recordings will be made using a MAC 5500 or equivalent. Each ECG trace will be labelled with the study number, participant number, participant year of birth. An Investigator will provide an interpretation of each tracing. Clinically significant abnormalities will be recorded on the AE page. Normal ranges for 12-lead ECG parameters are presented in [Appendix 2](#).

10.7.1.3.4 Stool Bacteriology

Stool samples of up to 10 g of stool will be collected for stool bacteriology (vaccine strains) in appropriate stool collection kits at the timepoints specified in Table 10.7.1.

Detailed sample collection and processing instructions will be documented in the SHM.

10.7.1.3.5 Blood Cultures

Blood samples will be collected (as specified in Table 10.7.1) for blood cultures to be performed to identify ZH9 and/or ZH9PA only if the participant experiences defined symptoms (e.g., fever greater than 37.8°C, WBC $>20 \times 10^9$ cells/L, respiratory rate >25 breaths per min, pulse rate >130 bpm) or clinically indicated. 8-10 ml of blood will be collection into bottles enriched with Aro. Detailed sample collection and processing instructions will be documented in the SHM.

10.7.1.3.6 Concomitant Medication

All prior and concomitant medications taken during the study will be recorded in the participant's eCRF (see [Section 10.6.10](#)).

10.7.2 Appropriateness of Measurements

All measurements performed in the study are standard measurements.

The total volume of blood to be collected from each participant during the study (approximately 388 mL) is considered acceptable ([Table 10.7.2](#)). If repeat or additional samples are required, the volume of blood taken will not exceed 500 mL.

Table 10.7.2 Summary of Blood Volume

Procedure	Visit	No. of Samples	Blood Volume per Sample (mL)
Biochemistry	Screening ¹	1	3.5
	Day 0	1	3.5
	Day 7	1	3.5
	Day 21	1	3.5
	Day 28	1	3.5
	Day 42	1	3.5
	Day 49	1	3.5
	Day 84 ²	1	3.5
Haematology	Screening	1	3.0
	Day 0	1	3.0
	Day 7	1	3.0
	Day 21	1	3.0
	Day 28	1	3.0
	Day 42	1	3.0
	Day 49	1	3.0
	Day 84	1	3.0
PD Assessment – PBMC/ALS assay	Day 0	1	64
	Day 7	1	64
	Day 28	1	64
	Day 49	1	64
PD Assessment – Serum Ig responses	Day 0	1	20
	Day 21	1	20
	Day 42	1	20
	Day 84	1	20
Total Blood Volume³			388

¹ From the biochemistry blood sample collected at the Screening visit, the serum pregnancy test (for all female participants only), serum FSH (for postmenopausal female participants only) and virology screen (HBsAg, HCV Ab, and HIV) will be analysed from the same serum sample.

² From the biochemistry blood sample collected at Day 84, the serum pregnancy test (for all female participants only) will be analysed from the same serum sample.

³ The exact volumes of each sample may change but the total volume of blood drawn for any participant will not exceed 500 mL. This total blood volume does not include blood samples required to be collected for performing blood cultures as specified in Table 10.7.1, and any repeat/unscheduled/additional blood sample collections required at the discretion of the Investigator/deputy.

10.7.3 Pharmacodynamic Assessments

The following PD blood samples will be collected at the time-points specified in Table 10.7.1.

- Serum Ig Responses
- PBMC for ALS assay

Detailed sample collection and processing instructions will be documented in the SHM.

The IgG and IgA responses to four antigens (LPS O:9, LPS O:2; H:d, H:a) will be determined by a validated enzyme-linked immunosorbent assay (ELISA) end point titre method.

PBMC will be cultured for 72 hours (+/- 3 hours) and the concentration of IgA in the supernatant specific for the same four antigens will be determined by a validated ELISA end point titre method.

10.7.4 Other Assessments

Not applicable.

10.8 Data Quality Assurance

At the time the study is initiated, a representative of the Sponsor will review the final protocol and eCRFs with the Principal Investigator and site staff. During the course of the study the Monitor will visit the Clinical Unit to check the completeness of the participants records (including the volunteer (participant) master files (VMF), laboratory and 12-lead ECG print-outs), the accuracy of entries into the eCRFs, the adherence to the final protocol and to ICH GCP E6 (R2) guidelines^[3], the progress of enrolment and also to ensure the storage, handling and accountability of the IMP. The Principal Investigator and key study personnel will be available to assist the Monitor during these visits.

The Principal Investigator will give the Monitor, Auditor(s), the REC, and the MHRA direct access to relevant clinical records to confirm their consistency with the eCRF entries. No information in these records about the identity of the participants will leave Simbec-Orion. The Sponsor will maintain the confidentiality of all participant records, in line with Section 6.10 of the ICH GCP E6 (R2) guidelines^[3] and the General Data Protection Regulation (GDPR) European Union (EU) 2016_679^[14].

Study data will be fully documented in the eCRFs, study log books and paper source files. Signatures (dated via audit trail) will be given to account for all interventions in the study by research staff.

Source data is all information in original records and certified copies of original records of clinical findings, observations, or other activities in a clinical study necessary for the

reconstruction and evaluation of the study. Source data are contained in source documents (original records or certified copies).

For the purposes of this study the source data will be recorded as detailed in [Table 10.8.1](#).

Table 10.8.1 Summary of Source Documentation Location

Data	Source Document			
	VMF	eCRF ⁴	Paper Source File	Log Book
Evidence of healthy participant status for entry into clinical study	X			
Demographic data ¹	X	X		
Medical history	X			
Inclusion and exclusion criteria		X		
Informed consents ²	X	X		
Participant participation in the clinical study	X	X		
Participant number in the clinical study		X	X	
Adverse events		X		
Previous and on-going therapy	X			
Concomitant therapy		X		
Results of study examinations (e.g., 12-lead ECGs, vital signs and laboratory safety tests) ³		X	X	
Study visit dates		X		
Administration of IMP		X	X	
Serum PD sample collection times		X		
Serum PD sample tracking				X
Evidence of handwashing training				X
Sentinel dosing 24-hour telephone call				X

1. Only year of birth will be captured in the eCRF

2. Copies of the informed consent form should be present in the VMF. The original informed consent forms will be maintained in the study officer file during the clinical phase and will then be transferred to the Project Manager for archiving with the Investigator site file at the end of the study.

3. The 12-lead ECG trace and laboratory safety test print-out will be stored in the paper source file.

4. In the event of eCRF technical issues source data will be located in the paper source file.

The above table indicates where source data will be recorded but for completeness the following information will also be recorded in the VMF:

- Clinical study code.
- Study visit dates (pre-dose; post-dose).
- IMP administration (date of last dose).
- Results of any key safety and efficacy measures from the clinical study that, in the opinion of an Investigator, should be noted.
- Any concomitant medications used to treat the participant during the study that should be noted.

The data collected in the eCRFs during the study will be subject to quality control checking by clinical staff prior to sign off.

Designated investigator staff will enter the data required by the protocol into the eCRFs using fully validated software that conforms to 21 CFR Part 11 requirements. Staff will not be given access to the eCRF until they have been trained. Automatic validation programs check for data discrepancies and, by generating appropriate error messages, allow the data to be confirmed or corrected before transfer of the data to the Biometrics group. The Investigator must certify that the data entered into the eCRF are complete and accurate.

The study will be subject to an independent audit by the Simbec-Orion Quality Assurance Unit as outlined in Simbec-Orion SOP BD/324/9/01.

Independent clinical quality assurance audits may be performed at any time during or following completion of the study by the Sponsor, or its authorised agents, and Regulatory Authorities and/or the REC.

10.9 Statistical Methods and Determination of Sample Size

10.9.1 Statistical and Analytical Plan

A statistical analysis plan (SAP) will be written by Simbec-Orion and agreed by Prokarium prior to the locking of the database and subsequent reporting of the study data.

10.9.1.1 Study Variables/Endpoints

Primary Endpoint

- Local and systemic reactogenicity up to Day 84 as assessed by adverse events, laboratory safety tests (biochemistry, haematology, urinalysis), vital signs and physical examination.

Secondary Endpoints

- Local and systemic reactogenicity; from Day 85 to Day 224 as assessed by adverse events, laboratory safety tests (biochemistry, haematology, urinalysis) if undertaken for cause; vital signs if undertaken for cause; physical exam if undertaken for cause.
- Concentrations of specific serum IgA and IgG antibodies to LPS O:2 and O:9, flagellin H:a and H:d.
- Fold increase in specific serum IgA and IgG antibody concentrations, in individual participants, against the antigens LPS O:2 and O:9, flagellin H:a and H:d.
- Concentrations of specific mucosal IgA antibodies in lymphocyte supernatant (ALS) assays, in individual participants, against antigens LPS O:2 and O:9, flagellin H:a and H:d.
- Seroconversion rate (proportion of participants with 4-fold increase above baseline at any time post vaccination) against each of the above antigens.
- Fold increase in specific mucosal IgA antibodies in lymphocyte supernatant (ALS) assays, in individual participants, against the antigens LPS O:2 and O:9, flagellin H:a and H:d.

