Each cohort will start with a sentinel group that will consist of 2 participants, 1 will receive placebo and 1 will receive the relevant vaccine for that cohort. No further participants will be dosed until 24 hours after the second participant has received his/her dose. The rest of the cohort will be dosed provided there are no safety issues identified by the Investigator. This design allows maintenance of the “blind” until Day 70.

The clinical phase is anticipated to take place in Q4 2019 and Q2 2020. The end of the study is defined as last participant last visit.

The study will take place in the Clinical Pharmacology Unit of Simbec-Orion (Clinical Unit) under full medical and nursing supervision.

A schedule of all study assessments is provided in [Table 10.7.1](#).

Screening (Day -28 to Day -1)

Screening assessments will be performed from Day -28 to Day -1 to ensure the eligibility of participants. Assessments will be performed as per [Table 10.7.1](#).

Treatment Period (Day 0 to Day 84)

Participants will be admitted to the Clinical Unit on the morning of Day 0 with confirmation of eligibility and baseline assessments performed as per [Table 10.7.1](#). Following a 90 minute (min) fast prior to dose administration, participants will receive the first dose on Day 0, and then continue to fast for a further 90 mins post dose administration; water will be allowed. Following the completion of the 4h post-dose assessments and at the discretion of the Investigator, the participants will be discharged from the Clinical Unit. Participants will return to the Clinical Unit on Day 3 for safety assessments as per [Table 10.7.1](#). For the 7 days following the first dosing visit (Day 1 to Day 7) participants will be required to record their body temperature at home twice a day i.e. once in the morning and once in the evening (a thermometer and a diary will be provided to record body temperature). Participants will return to the Clinical Unit on Day 7 with the diary and to give a blood sample for the peripheral blood mononuclear cells (PBMC)/ALS assay; assessments will be performed as per [Table 10.7.1](#). Participants will return to the Clinical Unit on Day 14 for safety assessments; assessments will be performed as per [Table 10.7.1](#).

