10.9.1.3.3 Safety Data

All safety data will be listed, in addition:

AEs: All AEs will be coded using the Medical Dictionary for Regulatory Activities (MedDRA) dictionary (the most up to date version will be used and this will be documented in the DMP)

All AEs, including those which occurred prior to receiving the first dose of IMP, will be listed. Only treatment emergent adverse events (TEAEs), i.e., existing conditions that worsen or events that occur during the course of the study after administration of IMP, will be included within the summary tables. AE summaries will be presented by treatment, all active treatments combined and overall.

An overall summary of AEs will be produced including the number of TEAEs; the number and % of participants reporting at least 1 TEAE, serious TEAE, TEAE leading to withdrawal from the study; the number and % of participants reporting TEAEs by severity and relationship to IMP.

The number of TEAEs and the number and % of participants reporting at least 1 TEAE will be tabulated by system organ class (SOC) and preferred term. A participant reporting multiple episodes of a particular AE will only contribute 1 count towards the corresponding SOC and preferred term.

The number of TEAEs and the number and % of participants reporting at least 1 TEAE will be tabulated by preferred term and sorted by descending frequency on the total number of participants with that AE. A participant reporting multiple episodes of a particular AE within a treatment period will only contribute 1 count towards the corresponding preferred term.

In addition, the number and % of participants reporting TEAEs will be tabulated by maximum severity and strongest relationship to IMP. For the summary of TEAEs by severity, if a participant has multiple events occurring within the same SOC or preferred term the event with the highest severity will be counted. Similarly, for TEAEs by relationship to IMP, if a participant has multiple events occurring within the same SOC or preferred term, the event with the highest association to IMP will be counted.

The incidence of TEAEs will be compared between treatments using Fisher's Exact Test (or an alternative statistical test if appropriate).

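### The primary endpoint is reactogenicity to Day 84, but the comparison planned for it tests all-cause TEAEs over the whole study, which dilutes any acute vaccine reaction

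*Combined protocol and SAP*

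**What the plan says.** The primary endpoint in Section 10.9.1.1 is "Local and systemic reactogenicity up to Day 84 as assessed by adverse events, laboratory safety tests", vital signs and physical examination. The first secondary endpoint carries the same label for the later period: "Local and systemic reactogenicity; from Day 85 to Day 224 as assessed by adverse events". Neither local nor systemic is defined for this oral vaccine.

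Section 10.9.1.3.3 builds its AE summary tables on TEAEs, meaning "existing conditions that worsen or events that occur during the course of the study after administration of IMP". Their number, and the participants with at least one, "will be tabulated by system organ class (SOC) and preferred term". A participant with repeated episodes counts once per SOC and once per preferred term. In addition, "the number and % of participants reporting TEAEs will be tabulated by maximum severity and strongest relationship to IMP". The incidence of TEAEs is then compared between treatments with Fisher's exact test. The section does not say which events enter that test, and it sets no onset window and no Day 84 limit.

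Elsewhere the protocol does work with a 7-day post-dose period. Home temperature is recorded for 7 days after each dose (Section 10.1 and the footnotes to Table 10.7.1), and the escalation reviews use safety data to Day 7 (Sections 10.1 and 10.2.1). Section 10.9.1 defers to a separate SAP, to be agreed before database lock, which is not among the documents.

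**The concern.** Reactogenicity ordinarily means reactions that follow a dose. The planned comparison instead counts any event at any time after the first dose, so a cold in Week 10 makes a participant a case just as vomiting on the evening of dosing does. When many placebo participants have at least one event, little room is left for a vaccine effect to show.

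The missing Day 84 cut adds a second problem. Up to Day 84, AEs are sought at clinic visits. Afterwards there are two telephone calls, on Days 154 and 224, which according to Section 10.1 review AEs that led to contact with a healthcare professional. One table over the whole study therefore merges two endpoints and two ways of finding events.

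With 6 to 12 participants per active arm, sensitivity is scarce. If the endpoint is not made operational before unblinding, the choice of events and window may be made after the data are seen.

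**Working it through.** **No planned figure to reproduce.** Section 10.9.2 states that the sample size has no formal statistical basis. The cohort sizes give 6 + 12 + 12 = 30 active and 3 + 6 + 6 = 15 placebo, 45 in all.

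**Share of the period close to a dose.** Doses are on Days 0, 21 and 42. Days 0–7, 21–28 and 42–49 are 3 × 8 = 24 days. Days 0 to 84 are 85 days. That leaves 85 − 24 = 61 days (72%) outside any 0–7 day window.

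**Illustrative power.** These inputs are assumptions, because the documents give no rates:
- background AEs at a constant rate of λ per participant per 85 days, with λ = 1 as the middle case;
- a vaccine reaction in r = 50% of active participants, always within 7 days of a dose, and in no placebo participant;
- Fisher's exact test, two-sided at 5% (the protocol states neither level nor sidedness);
- placebo pooled over cohorts, except in the last column.

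Formulas, for d days at risk:
- placebo: b = 1 − exp(−λd/85)
- active: a = 1 − (1 − b)(1 − r)
- risk difference: a − b = r(1 − b)
- power: the sum of binomial probabilities over all outcomes with Fisher p ≤ 0.05

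For λ = 1:
- Days 0–84: b = 1 − exp(−1) = 0.632; a = 1 − 0.368 × 0.5 = 0.816; difference 0.184.
- Days 0–7 after doses: b = 1 − exp(−24/85) = 0.246; a = 1 − 0.754 × 0.5 = 0.623; difference 0.377.

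| Events counted | Active v placebo | 12 v 15 | 30 v 15 | 12 v 6 (within cohort) |
|---|---|---|---|---|
| Any TEAE, Days 0–84 | 82% v 63% | 0.15 | 0.21 | 0.08 |
| Onset Days 0–7 after a dose | 62% v 25% | 0.40 | 0.60 | 0.24 |

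For 12 v 15, the window raises power from 0.26 to 0.58 if λ = 0.5 and from 0.07 to 0.30 if λ = 1.5.

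**Second parameterisation, to show the missing Day 84 cut.** Take r = 40%, a 40% background risk over 84 days at constant hazard, three 7-day windows (21 days), and 30 v 15:

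| Period | Placebo | Active | Power |
|---|---|---|---|
| 21 window days | 1 − 0.6^(21/84) = 0.12 | 1 − 0.88 × 0.6 = 0.47 | 0.63 |
| 84 days | 0.40 | 1 − 0.6 × 0.6 = 0.64 | 0.27 |
| 224 days | 1 − 0.6^(224/84) = 0.74 | 0.85 | 0.105 |

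The 224-day row probably overstates the loss, because follow-up by telephone should record fewer background events than clinic visits. The direction is the same across all the assumptions tried.

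**The case against.** **Much of what is wanted is already tabulated.** A reader might infer that the plan has no gut summary, or that the named endpoint is never produced. The documents do not support that. The SOC table gives a once-per-participant gastrointestinal row that recombines the separate preferred terms. The severity table takes the worst event within an SOC. The relationship table lets an investigator's causality judgement remove some background illness. This stands, and it narrows the gap. What remains is that no row groups systemic reactions, none of these tables is limited in time, and none is named as the variable for Fisher's test. The counting rule in the preferred-term table does mention a treatment period, but it governs repeat episodes and excludes nothing after Day 84.

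**Later doses.** AE contact thins out over the schedule. "Participants will return to the Clinical Unit on Day 14 for safety assessments" applies after the first dose only, and the longest gaps between AE contacts are 7 days after dose 1, 14 after dose 2 (Day 28 to 42) and 21 after dose 3 (Day 49 to 70). A reader might infer that later doses will look better tolerated. No between-dose comparison is planned, and the schedule is the same for active and placebo, so this is not a fault in the plan.

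**Bias.** Background events do not distort the direction of a randomised, placebo-controlled contrast. They shrink it.

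**The illustration favours the window.** It assumes that every reaction falls within 7 days, which the documents do not establish for live strains; Section 10.3 keeps open a theoretical risk of systemic infection. It also assumes that Fisher's test is applied to any TEAE, whereas the text says only TEAE incidence. Both points are fair, and they are why the all-TEAE tables must stay.

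**The SAP is still to come.** It could supply the definitions. As written, the protocol gives it none to implement.

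**Conclusion.** The point holds in this form: the comparison planned for the primary endpoint is all-cause, unwindowed and not cut at Day 84, so it is less sensitive to reactogenicity than the data allow. The existing SOC, severity and relationship tables offset this only in part. The cost is sensitivity, not validity.

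Under the middle assumption, restricting to Days 0–7 after doses doubles the risk difference (0.184 to 0.377). Power rises from 0.15 to 0.40 for a 12-participant arm against pooled placebo and from 0.21 to 0.60 for all active combined. Within a cohort it stays low (0.08 to 0.24), so cohort-level tests would not be informative either way. These sizes depend on rates that the documents do not give and on reactions being early. This is an improvement that should be made before unblinding, not a defect that undermines the trial.

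**What to change.** Before unblinding, in Section 10.9.1.3.3 and carried into the SAP:

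1. Cut the primary TEAE tables at Day 84 and tabulate Days 85 to 224 separately.
2. Derive two variables from AEs already collected with onset date and time: local (any gastrointestinal SOC event) and systemic (a preferred-term list fixed in advance), each with onset on Days 0–7 after any dose. Summarise them by treatment and maximum severity. Compare each active arm, and all active combined, with pooled placebo by Fisher's test, and give cohort-level counts descriptively.
3. Keep the all-TEAE and relationship tables alongside, so that later reactions to the live strains remain visible.

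The cost is a SAP derivation and a few tables, with no new visits, samples or participants. The downsides are that a term list and a window must be pre-specified, and that reactions after Day 7 will appear only in the all-TEAE tables.
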